### **THROMBOCYTOPENIA:**

Definition: <100,000 platelets/mm^3.

### **LEUKOPENIA:**

Definition: <3,000 white blood cells/mm^3. Exclude drug causes.

This is exactly as described, WBC <3,000/mm^3. The presence of an absolute lymphopenia does not count in the SLEDAI. A note of caution, do not confuse this WBC with that used to satisfy the ACR criteria for SLE which is WBC <3,500/mm^3.

With regard to current use of possible offending drugs, the following guidelines are to be considered:

**Appendix 10**  
**Systemic Lupus Erythematosus Disease Activity Index**  
**(SLEDAI-2K) (cont.)**

1. The nadir after cyclophosphamide, i.e., low WBC at 10 days after receiving cyclophosphamide in a patient known to have a WBC  $\geq$  3,000 at the time of receiving cyclophosphamide should not be counted.
2. Do not score leukopenia appearing after initiation of a new medication known to be associated with leukopenia, such as azathioprine or sulfa drugs. If the patient develops a WBC  $<$ 3000 while taking drugs which may cause leukopenia, score this only if the dosage of medication is unchanged since the last WBC determination.

## Appendix 11 SELENA-SLEDAI FLARE INDEX (SFI)

(Can be used with any version of the SLEDAI)

Mild or Moderate Flare	Severe Flare
Increase in SLEDAI by $\geq 3$ New or worse: Rash (discoid, photosensitive, profundus, cutaneous vasculitis, bullous lupus) Nasopharyngeal ulcers Pleuritis Pericarditis Arthritis Fever (SLE)	Increase in SLEDAI to $> 12$ New or worse (requiring doubling of prednisone, prednisone $> 0.5$ mg/kg/day, or hospitalization): CNS-SLE Vasculitis Nephritis Myositis Platelets $< 60,000/\text{mm}^3$ Hemolytic anemia: Hb $< 7\text{g/dL}$ or decrease of Hb by $> 3$ g/dL
Increase in Prednisone, but not to $>0.5$ mg/kg/day	Prednisone $> 0.5$ mg/kg/day
Added NSAID or hydroxychloroquine for disease activity	New cyclophosphamide, azathioprine, methotrexate, mycophenolate mofetil, or hospitalization (for SLE)
Increase in Physician's Global Assessment by $\geq 1.0$ , but not to more than 2.5	Increase in Physician's Global Assessment to $> 2.5$

Buyon JP et al. The Effect of Combined Estrogen and Progesterone Hormone Replacement Therapy on Disease Activity in Systemic Lupus Erythematosus: A Randomized Trial. *Ann Internal Med* 2005;142:953-62.

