#### **4.1.1 Inclusion Criteria**

Patients must meet all of the following criteria for study entry:

- Signed Informed Consent Form
- Age 18–75 years, inclusive
- Able to comply with the study protocol
- Fulfillment of SLE classification criteria according to either the current American College of Rheumatology (ACR) or Systemic Lupus International Collaborating Clinics (SLICC) criteria at any time prior to or at screening (see Appendix 5 and Appendix 6, respectively)
- At least one serologic marker of SLE at screening as follows:
  - Positive antinuclear antibody (ANA) test by immunofluorescent assay with titer  $\geq 1:80$ ; OR
  - Positive anti-double-stranded DNA (anti-dsDNA) antibodies; OR

- Positive anti-Smith antibody
- At both screening and Day 1, moderate to severe active SLE, defined as meeting all of the following unless indicated otherwise:
  - SLEDAI-2K score  $\geq 8$  (at screening only) with clinical SLEDAI-2K score  $\geq 4.0$  (at both screening and Day 1) (see [Appendix 10](#))
  - Physician’s Global Assessment  $\geq 1.0$  (out of 3) (see [Appendix 15](#))
  - Currently receiving at least one standard oral treatment (*e.g.*, corticosteroids, anti-malarials, and/or immunosuppressants) for SLE within the dose ranges, as specified below (see [Appendix 18](#)):
    - If on an OCS, the dose must be  $\leq 40$  mg/day prednisone (or equivalent, see [Appendix 18](#)) and must have been stable for at least 2 weeks prior to screening as well as during screening
    - If on anti-malarial or *immunosuppressant* therapies, may only be receiving medications from the following list within the specified dose range; dose and route of administration must be stable for 8 weeks prior to screening as well as during screening:
      - Azathioprine: 1 to 2.5 mg/kg/day
      - Methotrexate: 7.5 to 25 mg/week
      - Mycophenolate mofetil: 500 to 3000 mg/day
      - Mycophenolic sodium: 360 to 2160 mg/day
      - Hydroxychloroquine: 200 to 400 mg/day
      - Chloroquine: 100 to 250 mg/day
      - Quinacrine: 100 to 200 mg/day
      - Other: Consult with Medical Monitor

Note: Any combination of azathioprine, methotrexate, mycophenolate mofetil, or mycophenolic sodium is prohibited.

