#### **4.3.2.3.3 Burst Treatment**

In the case of increased disease activity, the patient will have the opportunity to receive burst treatment, in addition to the study treatment, during the defined burst treatment window (see [Figure 1](#)). The patient should return to the clinic, either at a scheduled study visit or unscheduled flare visit, to be evaluated and to receive an increase or new dose of oral prednisone as follows:

- Burst Window 1 (Weeks 0 to 10): An increase or new dose of oral prednisone up to 40 mg/day (or equivalent; see [Appendix 18](#))
- Burst Window 2 (Weeks 24 to 34): An increase or new dose in oral prednisone up to 20 mg/day (or equivalent; see [Appendix 18](#))

When using corticosteroids as a burst treatment, the investigator will temporarily increase the dose of corticosteroids and then taper the patient back down to their previous corticosteroid dose *used prior to the initiation of the burst*, all over the course of 2 weeks. Patients will continue to receive their designated dose of study treatment (see Section [4.3.2](#)) during the burst treatment. The previous corticosteroid dose is defined as the dose of corticosteroids taken for the 2 weeks prior to the burst (if the dose changed during the 2 weeks, the investigator may choose which dose to use). If the patient was not previously on corticosteroids, the investigator will taper the patient back off corticosteroids completely. If the patient was on a corticosteroid-tapering schedule at the time of the burst treatment, the investigator will revise the tapering schedule as necessary to meet the target OCS dose ( $< 10$  mg/day and  $\leq$  Day 1 dose) by the end of the taper window, *if clinically appropriate*.

Patients may receive corticosteroids for emergent illness other than SLE (*e.g.*, trauma, asthma) or if clinically warranted to prevent adrenal crisis (*e.g.*, prior to surgery). If possible, treatment in these cases should last no more than 7 days.

Any dose of steroid higher than the maximum burst levels above, any failure to taper the burst down to the previous level over the course of 2 weeks, or any necessity for additional burst treatments for increased SLE-related activity (either a second treatment within the burst window or a burst treatment outside the burst window), as determined by the investigator, will be recorded in the Steroid and immunosuppressant eCRF.

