#### **4.5.8.2 Systemic Lupus Erythematosus Disease Activity Index 2000 (SLEDAI-2K) and SELENA-SLEDAI Flare Index (SFI)**

The SLEDAI-2K will be used to approximate disease activity for entry into the study and at every subsequent study visit (see [Appendix 10](#)).

SLEDAI-2K measures disease activity at the visit or within the preceding 28 days. Detailed instructions and training on the use of the SLEDAI-2K will be provided during training sessions at each investigator meeting, and through online resources. It is critical that investigators have a thorough understanding of both *the BILAG and SLEDAI-2K* instruments and the differences between them.

The SFI categorizes SLE flare as “mild or moderate” or “severe” based on 6 variables ([Buyon et al, 2005](#); [Petri et al. 1999](#); [Petri et al. 2005](#)):

- Change in SELENA-SLEDAI (or SLEDAI-2K) score from the most recent assessment to current
- Change in signs or symptoms of disease activity
- Change in prednisone dosage
- Use of new medications for disease activity or hospitalization
- Change in PGA score
- Hospitalization for activity (severe flare only)

The *SFI* will be modified such that severe flares *defined only by the occurrence of an increase in SLEDAI-2K score to > 12* will be excluded. One or more other items defining severe flare in the SFI needed to be present for a severe flare to be recorded. This modification was made because patients entering the trial with high disease activity

(e.g.,  $\geq 11$ ) could too easily trigger a severe flare by minor increases in the SLEDAI-2K score.

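### The SFI prednisone items carry no lupus attribution, so permitted non-SLE steroid courses score as SLE flares in two exploratory endpoints

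*Combined protocol and SAP*

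**What the plan says.** - **Appendix 11, prednisone items.** The mild/moderate column lists "Increase in Prednisone, but not to $>0.5$ mg/kg/day". The severe column has a stand-alone item for prednisone above 0.5 mg/kg/day. Neither requires a reason.
- **Appendix 11, neighbouring items.** "Added NSAID or hydroxychloroquine for disease activity" is tied to lupus. So is hospitalization in the severe new-drug item, and fever is marked as SLE fever. Where prednisone appears inside the severe organ-manifestation item, it is tied to those manifestations.
- **Section 4.5.8.2.** The variable list has "Change in prednisone dosage" without a qualifier, next to "Use of new medications for disease activity or hospitalization". The section changes the index in one respect only: a severe flare may not rest solely on a SLEDAI-2K rise above 12. Any one other severe item is still enough.
- **Section 4.3.2.3.3.** "Patients may receive corticosteroids for emergent illness other than SLE (*e.g.*, trauma, asthma) or if clinically warranted to prevent adrenal crisis", if possible for no more than 7 days.
- **Drug names.** Appendix 11 names hydroxychloroquine as the only anti-malarial and mofetil as the only mycophenolate. Section 4.1.1 also permits "Mycophenolic sodium: 360 to 2160 mg/day", chloroquine and quinacrine. Section 4.3.2.3.4 makes a new start of an immunosuppressant or anti-malarial for increased SLE activity escape therapy.
- **Use.** Section 6.4.3 lists time to first SFI flare and total SFI flares as exploratory endpoints. Table 1 uses both again under the exploratory biomarker objectives. Section 6 leaves scoring details to a Data Analysis Plan (DAP), which is not among the documents available.

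**The concern.** A treatment item works in a flare index because escalation prompted by lupus is evidence of a flare. A course for trauma or peri-operative cover is not. The prednisone items do not separate the two, and the protocol expressly allows the second kind.

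False events shorten the time to first flare in patients who had none, or had theirs later. They also add to the total count in every patient who has such a course. At stake is how two exploratory endpoints read, and any biomarker finding built on them.

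A smaller gap runs the other way. Starting mycophenolic sodium, chloroquine or quinacrine for lupus meets no SFI treatment item, while starting mycophenolate mofetil or hydroxychloroquine does.

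**Working it through.** The protocol gives no SFI flare rate, so there is no planned figure to reproduce. The check compares the texts, then adds arithmetic for scale.

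**1. Does the rule reach non-SLE courses?** Section 4.3.2.3.3 permits them. Appendix 11 counts a prednisone increase without asking why. The one modification in Section 4.5.8.2 concerns SLEDAI-2K alone. No other section takes these courses out of the SFI. As written, they count.

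**2. When would such a course be severe?** The dose exceeds the threshold when body weight < dose / 0.5:
- 40 mg/day: 40 / 0.5 = 80 kg
- 30 mg/day: 30 / 0.5 = 60 kg
- 20 mg/day: 20 / 0.5 = 40 kg

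The protocol states no dose for non-SLE courses; these are illustrations.

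**3. What would equal misclassification do?** These inputs are assumptions, not figures from the protocol: true risk of any flare by Week 48 of 60% and 40%, and a probability q of a false flare that is the same in both arms. The 80 per arm is from Section 6.1. Observed risk = 1 − (1 − p)(1 − q), so observed difference = (p1 − p2)(1 − q). Power is for a two-sided 0.05 comparison of two proportions (pooled normal approximation), as a stand-in for the planned Kaplan-Meier analysis.

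| q | Observed risks | Difference (points) | Power |
|---|---|---|---|
| 0 | 60.0% v 40.0% | 20.0 | 72% |
| 2% | 60.8% v 41.2% | 19.6 | 70% |
| 5% | 62.0% v 43.0% | 19.0 | 67.5% |
| 10% | 64.0% v 46.0% | 18.0 | 63% |

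**4. How many patients?** Patients with a false event number 80 × q, that is 1.6, 4 or 8 per arm for q of 2%, 5% or 10%. Those who change from no flare to flare number 80 × q × (1 − p). In the 40% arm that is 80 × 0.6 × q = 1.0, 2.4 or 4.8. The larger numbers bear on the flare count, the smaller ones on whether a patient ever flared.

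**5. Can the reason be recovered?** Section 4.3.2.3.4 asks for the reason for additional corticosteroids, whatever it is, on the Corticosteroid Medication eCRF. Section 4.4 asks for the indication of every concomitant drug. The similar sentence in Section 4.3.2.3.3 covers only use outside the steroid rules, so on its own it might miss a permitted non-SLE course. The other two sections close that gap.

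**6. Do the omitted drugs lose whole episodes?** Only in part. The same episode still counts if SLEDAI rises by 3 or more, if rash, arthritis or serositis is new or worse, if prednisone rises, or if the Physician's Global Assessment rises enough. It is lost only when none of these, and no other item, is met.

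**The case against.** The strongest reply is that scoring of disease-activity instruments is deferred to the DAP, where an attribution rule may exist. Appendix 11 reproduces a cited index, Section 4.5.8.2 describes it as classifying SLE flare, and assessors are trained or certified under Section 4.5.8. A trained assessor might never score an asthma course as lupus. This has weight, and the DAP cannot be checked here. But the protocol's stated rule gives a wrong result when followed, and sites score the SFI at visits from Appendix 11. If they record only the flare category, a later derivation may not be able to undo it; the documents do not say which is recorded.

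Frequency is the second reply, and it stands. Section 4.1.2 excludes chronic conditions, asthma among them, that needed steroids in the 24 weeks before screening or are likely to need them on study. Rates of 5% to 10% may well be too high.

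Third, Appendix 11 says prednisone, not corticosteroid. Read strictly, a non-SLE course of another agent would not count. The problem is certain for courses given as prednisone, and extends to others only if equivalents are meant.

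A reader might infer three stronger claims that the documents do not support:
- **Bias between arms.** This needs treatment to change the rate of non-lupus events that lead to steroids. Infection and bleeding are handled in Table 4 by withholding study treatment, and nothing links them to steroid courses.
- **All four flare endpoints are affected.** Two are defined by the BILAG, not the SFI, and are untouched.
- **Lupus escape treatments go uncounted.** This holds for the treatment items alone, as step 6 shows. The pool is also small: Section 4.1.1 bars combining the four immunosuppressants, and Section 4.4.1.1 discourages starting an anti-malarial on study.

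**Conclusion.** The point holds, and it is minor. As written, the SFI counts permitted non-lupus prednisone courses as SLE flares, some of them severe. It touches the two exploratory SFI endpoints and the exploratory biomarker analyses that use them. The primary SRI-4 analysis and the secondary endpoints are not affected.

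The size cannot be fixed from the documents. On the assumed 60% and 40% risks, a false-flare probability of 2% to 10%, equal across arms, costs between 0.4 and 2.0 points of a 20-point difference and takes power from 72% to between 70% and 63%. The lower end is the more plausible, given the exclusion in Section 4.1.2. The direction is toward the null if the arms are alike; there is no basis for assuming that they differ.

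The drug-name gap is secondary. It bears only on episodes that meet no other SFI item.

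**What to change.** In Appendix 11, Section 4.5.8.2 and the flare derivation, count the two stand-alone prednisone items only when the increase, in prednisone or equivalent, is for SLE activity. Take the reason from the Corticosteroid Medication eCRF, with the concomitant-medication indication as a check. Keep the published scoring as a sensitivity analysis.

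As a minor addition, score a new start of mycophenolic sodium for SLE activity like mycophenolate mofetil, and a new start of chloroquine or quinacrine for SLE activity like hydroxychloroquine. Dose increases of drugs already taken are also escape therapy and would remain unscored, as in the published index; the derivation should say so.

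These changes concern scoring only and leave patient treatment as it is. The cost is a few words in two places and a small change to the derivation, with no new data item. The downside is a slight departure from the published wording, which the sensitivity analysis covers. The sponsor has already modified this index once, in Section 4.5.8.2.

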## Appendix 12 Glucocorticoid Toxicity Change Index

### COMPOSITE GLUCOCORTICOID TOXICITY CHANGE INDEX

1. Body mass index (BMI) (compared to baseline)
  - a) Improvement (in either direction) by more than 2 BMI units toward normal BMI (normal range = 18.5–24.9 kg/m^2)
  - b) No significant change (BMI remains within  $\pm 2$  BMI units compared with baseline) or BMI remains within the normal range
  - c) Moderate increase in BMI (increase by more than 2 but less than 5 BMI units to above the upper limit of normal BMI [24.9 kg/m^2])
  - d) Major increase in BMI (increase by more than 5 BMI units to above normal BMI [24.9 kg/m^2])
  
2. Glucose tolerance (compared to baseline)
  - a) Improvement in glucose tolerance:
    - HbA1c (glycosylated hemoglobin) declined  $> 10\%$  from baseline without medication increase
    - OR**
    - Decrease in diabetic medication without an increase in HbA1c of  $> 10\%$  or HbA1c  $< 5.7\%$
  - b) No significant change in glucose tolerance:
    - HbA1c within 10% of baseline or HbA1c  $< 5.7\%$  and no change in medication
    - OR**
    - HbA1c increased to  $> 10\%$  of baseline due to a decrease in medication
    - OR**
    - Improvement in glucose tolerance  $> 10\%$  due to an increase in medication
  - c) Worsening of glucose tolerance or medication status:
    - HbA1c increased to  $> 10\%$  and HbA1c  $> 5.7\%$  without a change in medication
    - OR**
    - Increase in diabetic medication with  $< 10\%$  increase in HbA1c
  - d) Worsening of glucose tolerance despite treatment:
    - HbA1c  $> 5.7\%$  and increased to  $> 10\%$  of baseline and an increase in diabetic medication

## Appendix 12 Glucocorticoid Toxicity Change Index (cont.)

3. Blood pressure (BP) (compared to baseline)
  - a) Improvement in BP:
    - Decrease in BP of  $> 10\%$  of baseline without medication increase

**OR**

    - Decrease in medication without an increase in BP of  $> 10\%$  or systolic BP  $\leq 120$  and diastolic BP  $\leq 85$
  - b) No significant change in BP:
    - BP within  $10\%$  of baseline or systolic BP  $\leq 120$  and diastolic BP  $\leq 85$  and no change in medication

**OR**

    - Deterioration in either systolic or diastolic BP  $> 10\%$  due to a decrease in medication

**OR**

    - An improvement in either systolic or diastolic BP of  $> 10\%$  due to an increase in medication
  - c) Worsening of hypertension:
    - Increase in BP of  $> 10\%$  such that the systolic BP exceeds 120 mmHg or the diastolic BP exceeds 85 mmHg without a change in medication

**OR**

    - Increase in anti-hypertensive medication without an improvement in BP  $> 10\%$
  - d) Worsening of hypertension despite treatment:
    - Increase in BP of  $> 10\%$  such that the systolic BP exceeds 120 mmHg or the diastolic BP exceeds 85 mmHg and an increase in medication
4. Hyperlipidemia (compared to baseline)
  - a) Improvement in lipids:
    - Decrease in low-density lipoprotein (LDL) concentration  $> 10\%$  of baseline without medication increase toward the target range

**OR**

    - Decrease in medication without an increase in LDL of  $> 10\%$  or LDL remains within target range

## Appendix 12 Glucocorticoid Toxicity Change Index (cont.)

- b) No significant change in LDL:
    - LDL within 10% of baseline or within the target range for patient and no change in medication
    - OR**
    - Increase in LDL > 10% due to a decrease in medication
    - OR**
    - Improvement in LDL of > 10% due to an increase in medication
  - c) Worsening of LDL or medication status:
    - Increase in LDL of > 10% to above target range without increase in medication
    - OR**
    - Increase in medication without > 10% change in LDL
  - d) Worsening of LDL despite treatment:
    - Increase in LDL of > 10% and an increase in medication
5. Steroid myopathy
- a) No steroid myopathy
  - b) Mild steroid myopathy (weakness without functional limitation)
  - c) Moderate steroid myopathy (weakness with functional limitation)
- See steroid myopathy definitions below.
6. Skin
- a) No skin toxicity
  - b) Mild
  - c) Moderate
- See skin definitions below.
7. Neuropsychiatric
- a) No neuropsychiatric symptoms
  - b) Mild
  - c) Moderate
- See neuropsychiatry definitions below.

## **Appendix 12 Glucocorticoid Toxicity Change Index (cont.)**

8. Infection (since last assessment)
  - a) No significant infection
  - b) Specific infections < Grade 3 (oral or vaginal candidiasis, uncomplicated zoster)
  - c) Grade 3See infection notes below.
  
9. Bone mineral density (BMD) (compared to baseline)
  - a) Improvement – increase in BMD by > 3%
  - b) No significant change (BMD between – 3% and + 3%)
  - c) Deterioration – decrease by  $\geq 3\%$% refers to total BMD in gms/cm^2  
If BMD not evaluated, then option “b” should be selected.

### **GLUCOCORTICOID-INDUCED MYOPATHY DEFINITIONS**

- Glucocorticoid-induced myopathy is defined as mild symmetrical weakness of the proximal muscles and/or neck flexors associated with steroid therapy and not due to any other apparent cause. Muscle enzymes are typically within normal limits.
- Mild and moderate myopathy are defined by muscle strength of 4 on the standard Medical Research Council strength testing scale. A 4 means weaker than normal but greater than anti-gravity strength.
- “Mild” is Grade 4 weakness that does not functionally limit the patient.
- “Moderate” is Grade 4 weakness that does impose functional limitations on the patient, interfering with normal daily activities.
- Note that inability to rise from a chair without assistance constitutes severe glucocorticoid-induced myopathy (Specific Domain)

### **SEVERITY OF GLUCOCORTICOID TOXICITY IN THE SKIN**

Manifestations to be considered:

- Acneiform rash
- Easy bruising
- Hirsutism
- Atrophy/striae
- Erosions/tears/ulcerations

## Appendix 12 Glucocorticoid Toxicity Change Index (cont.)

Skin 6b. Mild	Skin 6c. Moderate	Severe (Specific Domain)
Acneiform rash (Grades 1–2)	Acneiform rash (Grade 3)	Acneiform rash (Grade 4)
Easy bruising (Grade 1)	Easy bruising (Grade 2)	
Hirsutism (Grade 1)	Hirsutism (Grade 2)	
Atrophy/striae (Grade 1)	Atrophy/striae (Grade 2)	Atrophy/striae (Grade 3)
Erosions/tears/ulcerations (Grade 1)	Erosions/tears/ulcerations (Grade 2)	Erosions/tears/ulcerations (Grade 3)

### Acneiform rash

- Grade 1: Papules and/or pustules covering < 10% body surface area (BSA), which may or may not be associated with symptoms of pruritus or tenderness
- Grade 2: Papules and/or pustules covering 10%–30% BSA, which may or may not be associated with symptoms of pruritus or tenderness; associated with psychosocial impact; limiting instrumental activities of daily living (ADL)
- Grade 3: Papules and/or pustules covering > 30% BSA, which may or may not be associated with symptoms of pruritus or tenderness; limiting self-care ADL; associated with local superinfection with oral antibiotics indicated
- Grade 4: Papules and/or pustules covering any % BSA, which may or may not be associated with symptoms of pruritus or tenderness and are associated with extensive superinfection with intravenous (IV) antibiotics indicated; life-threatening consequences

